5. RANDOMIZATION

Survivors and their caregivers who meet the eligibility criteria, sign the informed consent form and complete all baseline assessments will immediately be randomized as a dyad to one of two trial arms by means of a computer-generated randomization table.

5.1 A total enrollment of 70 cancer survivors and their 70 primary caregivers is planned (70 dyads total, 35 dyads per trial arm).

5.2 The two trial arms will be as follows:

Trial Arm	Condition
1	Dyadic Exercise Intervention (EXCAP-PA) : Progressive walking and resistance exercise treatment, prescribed to both cancer survivors and their caregivers (daily walking and up to 7 times/week resistance prescription for 6 weeks). Cancer survivor and caregiver are also asked to discuss ways they can support one another in a) remaining adherent to exercise, and b) dealing with stress, including LGBT-specific minority stress.
2	Individual Exercise Intervention (EXCAP) : Progressive walking and resistance exercise treatment, prescribed solely to cancer survivors (daily walking and up to 7 times/week resistance prescription for 6 weeks). The caregiver is told not to change his/her exercise behavior in any way.

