The study chair, study coordinator, and Certified Exercise PhysiologistSM have received appropriate training, as well as password secured access to use the University of Rochester Medical Center's electronic patient scheduling and clinical information systems to obtain medical information and appropriate source documentation for research files.

- 6.3.3 During the consent meeting, all participants will be given a pedometer (or a fitness tracker such as the FitBit) and an Actigraph to wear for approximately 4-7 consecutive days before the baseline assessment. The pedometer (or fitness tracker) and actigraph will be collected at the baseline assessment and returned to all participants for approximately 4-7 days of monitoring prior to the post-intervention assessment.
- 6.3.4 The study team member will schedule a time for survivor and caregiver to return to the PEAK Lab to complete the baseline assessment. The study team member will make phone or e-mail contact with survivor and caregiver approximately 7 days before their scheduled baseline assessment to remind them to wear their pedometers (or fitness trackers) and actigraphs.

6.4 *Baseline assessment*

- 6.4.1 **All assessments will be done on all study participants (cancer survivors and their caregivers).** Survivors and caregivers can complete assessments either as a dyad or individually. The sequence of assessments will be the same at baseline and post-intervention.
- 6.4.2 **Blood draw.** At the baseline assessment (and again at the post-intervention assessment), blood sampling will be done to estimate hematocrit, hemoglobin, lymphocytes, monocytes, and biological endpoints of interest (serum amyloid A, CRP, cortisol, along with mRNA concentrations of these endpoints). Blood draws can be conducted with cancer survivor and caregiver together or separately, on the same day as the baseline assessment or up to a week before the baseline assessment. The consent form will include a section asking whether participants agree to have their samples biobanked for additional, future analyses. Participants will have the option to check yes or no to having their samples biobanked.

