6.4.5 **Physical function assessments.** Additionally, participants will be evaluated on **1)** body composition (bioelectrical impedance), **2)** heart rate variability, **3)** muscular strength (Handgrip Dynamometry, isokinetic knee flexion/ extension and shoulder diagonal), and **4)** aerobic capacity (6 minute walk test), in that order. All physiological fitness testing will be administered according to the Guidelines for Exercise Testing and Prescription (GETP) as outlined by the American College of Sports Medicine (ACSM). (See section 10.2 for additional details.)

6.4.6 Data from pedometers (or fitness trackers) and actigraphs will also be collected for analysis. Data from pedometers will be used to inform the walking prescription of the exercise interventions.

6.4.7 **Randomization.** Following completion of physical functioning assessments, dyads will be randomized to a trial arm. Instructions and an exercise kit for the home-based walking and progressive resistance exercise program will be given to survivors and caregivers together in Arm 1 and cancer survivors alone in Arm 2. Caregivers in Arm 2 will receive instructions and an exercise kit following the post-intervention assessment.

6.4.7.2 Cancer survivors and caregivers in dyads randomized to Arm 1 (EXCAP-PA) will each receive a home-based walking and progressive resistance exercise program to follow for a total duration of approximately 6 weeks. These dyads will be instructed in ways to use the exercise kits together. They will also meet briefly with a member of the study team, who will guide them through a discussion of barriers to exercise, ways they can support one another in remaining adherent to exercise, and ways of dealing with stress (including LGBT minority stress).

6.4.7.1 Cancer survivors in dyads randomized to Arm 2 (survivor-only EXCAP) will receive a home-based walking and progressive resistance exercise regimen to follow for a total duration of approximately 6 weeks. Caregivers in dyads randomized to Arm 2 will be told not to change their exercise behavior in any way, will not receive an exercise regimen to follow during the study period and will not discuss dyadic support with the cancer survivor.

6.5 **EXCAP:** Home-Based Walking and Progressive Resistance Exercise Program

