6.5.1 The Home-Based Walking and Progressive Resistance Exercise Program is designed by an Exercise Scientist certified by the American College of Sports Medicine (ACSM) and is in accordance with the guidelines for exercise testing and prescription as set forth by the ACSM.

6.5.2 The Home-Based Walking and Progressive Resistance Exercise Program will follow the guidelines listed below.

6.5.2.1 The Home-Based Walking Prescription will be based on a participant's (i.e., survivor's or caregiver's) baseline pedometer assessment. Participants will be given a pedometer (or fitness tracker) and encouraged to increase their total steps walked by a minimum of 5% a week during the 6-week intervention while maintaining a moderate intensity. [Note: Walking intensity will be monitored via the Rating of Perceived Exertion (RPE) Scale, which is a visual analog scale ranging from 1 = no exertion at all to 10 = very strong exertion. Participants will be instructed to aim for an RPE of 5-8, consistent with other studies of EXCAP for cancer survivors.] The upper threshold of the walking prescription of the EXCAP program will be 12,000 steps per day.

6.5.2.2 The Home-Based Progressive Resistance Prescription will be based on a participant's baseline isokinetic strength assessment. Participants will be instructed on the proper use of resistance bands. Participants will then be instructed to choose a resistance band with which they can perform 8-12 repetitions of 5 upper body resistance exercises (bicep curl, tricep extension, chest press, rows, and overhead press) and 5 lower body resistance exercises (leg curl, leg extension, squat, toe raises, and side bends), plus core strengthening exercises. Participants will be instructed to begin with 1 set of 8-12 repetitions at a moderate to challenging level (RPE 5-8), up to 7 times per week. Participants will be instructed to progressively increase to 4 sets for each exercise 3 times per week. (Note. Survivors and caregivers in Arm 1 will both be instructed in the proper methods for performing each exercise as a dyad. Cancer survivors in Arm 2 will be instructed in the proper methods for performing each exercise individually.)

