10.2.1.4 The **Pedometer** (or fitness tracker) will be used to assess duration of physical activity via steps walked during the time out of bed. Both pedometers and fitness trackers provide visual feedback of number of steps walked, and so can be used in the same fashion. The PEAK Lab is in the process of transitioning from standard pedometers to wearable fitness trackers.

10.2.1.4 **Heart Rate Variability** (HRV) will be measured using the Firstbeat® Bodyguard 2 to assess the HRV at the beginning of the first and the sixth intervention session. To measure HRV, participants will sit quietly for five minutes in the PEAK Lab wearing the Bodyguard 2 leads attached to their side and upper chest. Five biomarker outcomes will be assessed. Two time domains will be assessed including **SDNN** (the standard deviation of all normal R-R intervals measured between consecutive sinus beats) and **RMSSD** (the root mean square of successive differences between adjacent normal R-R intervals). Three frequency domains will be assessed including **RSA** (Respiratory Sinus Arrhythmia), **LF** (natural log of low frequency, total spectrum power of all NN intervals between 0.04 to 0.15Hz), and **LF/HF ratio** (the ratio of Low Frequency Total Spectrum Power of all NN Intervals Between .04 to .15 Hertz to High Frequency Total Spectrum Power of all NN Intervals between .15 to .40 Hertz).

10.2.2 A **6 Minute Walk** test will be used to assess aerobic capacity. This is a modified but still maximal measurement using a 6 minute walk protocol, generating a valid assessment while ensuring participant comfort. Participants are given a short warm up and cool down walking protocol in the test walking area in the University of Rochester PEAK Laboratory. Participants walk for a total of 6 minutes and cover as much distance as they can during this time. Upon completion of the test, the total distance walked is used to calculate an estimate of aerobic capacity (VO₂max; Maximal Oxygen Consumption). A physician (or physician’s designee) is available onsite in the hospital during testing of patients deemed high risk by the ACSM Certified Exercise PhysiologistSM, as outlined by the ACSM fitness testing guidelines.

10.2.3 Muscular fitness will be assessed using two measures: a handgrip dynamometer test and an isokinetic muscular strength test.

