11. CONFIDENTIALITY OF DATA AND DATA STORAGE

11.1 Data Collection Table

FORM	Baseline	Post Intervention
On Study Data (Demographic and clinical data)	X	
Clinical Record Information (Clinical data – survivor only)	X	
Medication Form	X	
Physical Activity Readiness Questionnaire (PAR-Q+)	X	
Profile of Mood States (POMS)	X	X
Aerobic Center Longitudinal Study Physical Activity Questionnaire (ACLS; 15-item physical activity history measure)	X	X
Patient Health Questionnaire - 9 (PHQ-9)	X	X
Spielberger State/Trait Anxiety Inventory (STAI Form Y-1)	X	X
Short Form Health Survey 12 (SF-12)	X	X
Dyadic Adjustment Scale – 7 (DAS-7)	X	X
Dyadic Support Questionnaire (DSQ)	X	X
PROMIS Patient-Reported Item Batteries	X	X
Insomnia Severity Index (ISI)	X	X
Multidimensional Fatigue Symptom Inventory (MFSI)	X	X
Heterosexism and Identity Questionnaire	X	X
Physician Interaction (PEPPI, THC, and SSE) Scales	X	X
Physiological Fitness Test Evaluations (6 min walk test, handgrip dynamometry, isokinetic strength test, bioelectrical impedance)	X	X
Heart Rate Variability (Firstbeat Bodyguard 2)	X	X
Biological Endpoints (via blood draw)	X	X
Pedometer (or fitness tracker)	Continuous (for those exercising)	Continuous (for those exercising)
Actigraphy	7 days before	7 days before
Daily Diary	Continuous (for those exercising)	Continuous (for those exercising)

- 11.2 All hardcopy research records will be stored onsite in the University of Rochester Medical Center, in the Cancer Control Unit and the PEAK Lab of the James P. Wilmot Cancer Institute. The Cancer Control Unit is located in the Saunders Research Building, in an office suite secured by electronic key cards. The PEAK Lab is located in the medical center and is also secured by electronic key cards. Offices within the Unit and the Lab are again secured by key and data is kept in locked file cabinets. Electronic research records are stored on the University of Rochester Medical Center's password secured and

Protocol date: 7/06/2020

firewall protected networks. These are the same methods of security used for patient medical records. Human serum samples are stored in locked freezers, within locked and alarmed laboratories that are accessible by key codes and electronic card swipes. All study data will be kept for a period of at least 6 years after the study and all reports and publications are complete.

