13. DATA ANALYSIS AND DATA MONITORING

13.1 Measures for the primary and secondary aims will be:

- 13.1.1 Cancer survivor's self-reported psychological distress (30 item POMS Total Score) at post-intervention (Primary Aim 1)
- 13.1.2 Cancer survivor's serum levels of stress-related biological endpoints (cortisol, serum amyloid A, C-reactive protein) at post-intervention (Secondary Aim 2)
- 13.1.3 Cancer survivor's received support from the caregiver (Dyadic Support Questionnaire) at post-intervention (Secondary Aim 3)
- 13.1.4 Cancer survivor's physical activity, as measured by actigraphy, at post-intervention (Secondary Aim 3)

13.2 Measures for the exploratory aim in caregivers will be:

- 13.2.1 Caregiver's self-reported psychological distress (30 item POMS Total Score) at post-intervention
- 13.2.2 Caregiver's serum levels of stress-related biological endpoints (cortisol, serum amyloid A, C-reactive protein) at post-intervention
- 13.2.3 Caregiver's received support from the cancer survivor (Dyadic Support Questionnaire) at post-intervention
- 13.2.4 Caregiver's physical activity, as measured by actigraphy, at post-intervention

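### Arm 2 caregivers are re-issued a visible step counter in the post-intervention monitoring week, which can shrink the exploratory caregiver activity contrast

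*Combined protocol and SAP*

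**What the plan says.** Section 6.3.3 provides that, at the consent meeting, "all participants will be given a pedometer (or a fitness tracker such as the FitBit) and an Actigraph" to wear for about 4-7 days before baseline. The devices are collected at baseline and then "returned to all participants for approximately 4-7 days of monitoring prior to the post-intervention assessment". Neither sentence excepts Arm 2 caregivers.

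Section 10.2.1.4 notes that "Both pedometers and fitness trackers provide visual feedback of number of steps walked". No masking of the display is described.

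The counter is also a treatment tool. Section 6.4.6 says "Data from pedometers will be used to inform the walking prescription of the exercise interventions". Section 6.5.2.1 has participants given a counter and "encouraged to increase their total steps walked by a minimum of 5% a week during the 6-week intervention". Section 6.9 and the Appendix list a pedometer among the contents of the exercise kit.

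For Arm 2, section 5.2 states: "The caregiver is told not to change his/her exercise behavior in any way". Section 6.4.7 holds back the kit from these caregivers until after the post-intervention assessment. In Table 11.1 the pedometer row reads "Continuous (for those exercising" in both columns.

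Section 13.2.4 lists "Caregiver's physical activity, as measured by actigraphy, at post-intervention" among the measures for the exploratory caregiver aim.

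**The concern.** Arm 2 caregivers are the no-exercise comparison group for caregiver activity. The plan keeps the kit, the program and the activity part of the diary away from them. Section 6.3.3 nevertheless puts one kit component, a device that shows a running step count, on them during the week in which their outcome activity is recorded. The Actigraph is worn in the same days, so any extra walking that the display prompts is recorded as control-arm activity.

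In Arm 1 the counter is part of the treatment and has been in use for weeks. In Arm 2 it reappears after weeks without it. If it prompts walking mainly in Arm 2, control activity moves towards Arm 1, and the caregiver contrast that might inform a later trial is understated.

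**Working it through.** **The plan's own figures.** The documents give no figure for reactivity to a display and no power statement for caregiver activity. The only stated power is for survivor POMS, and it reproduces. The ANCOVA residual SD is 13.01 × √(1 − 0.7²) = 9.29. With 30 per arm and a difference of 6.90, power is 80.7% (noncentral t, 57 df), against the stated 80%. No activity input enters that calculation.

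**Inputs for the scenarios**
- Arm 1 rise: at least 5% a week (6.5.2.1). The post actigraphy window is day 35 to day 42 (10.2.1.3), so five to six increments apply: 1.05⁵ − 1 = 27.6% and 1.05⁶ − 1 = 34.0%. This assumes that caregivers exactly meet the minimum.
- Reactivity r of Arm 2 caregivers in the post week: not in the documents. Assumed range 0-15% of habitual steps.

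**Scenario A: only Arm 2 reacts.** With Arm 1 rise g, the contrast left is g − r and the share lost is r/g.

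| r | g = 27.6%: left (share lost) | g = 34.0%: left (share lost) |
|---|---|---|
| 0% | 27.6 points (0%) | 34.0 points (0%) |
| 5% | 22.6 (18%) | 29.0 (15%) |
| 10% | 17.6 (36%) | 24.0 (29%) |
| 15% | 12.6 (54%) | 19.0 (44%) |

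**Scenario B: both arms react by the same proportion in the post week.** The contrast is (1 + r)(1 + g) − (1 + r) = (1 + r)g, which is 1.05 to 1.15 times the unreactive contrast for r of 5-15%. Nothing is lost.

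**Scenario C: the display also raises the baseline count, and Arm 1 reaches a target set from that count.** Arm 1 ends at (1 + r)(1 + g) of habitual steps and Arm 2 at 1 + r. The contrast is again (1 + r)g: 29.0-31.8 points for g = 27.6% and 35.7-39.1 points for g = 34.0%. Nothing is lost.

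**Sensitivity to g.** A larger Arm 1 rise makes the lost share in Scenario A smaller, and incomplete adherence makes it larger. The Appendix describes a weekly increase with an upper limit and an 8-week period, whereas 6.5.2.1 gives a minimum and 6 weeks. Those passages must be reconciled. The scenarios use 6.5.2.1 for illustration only.

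**Baseline week.** It precedes randomisation, so any display effect there is expected to be equal in the two arms. It alters within-person change: with a fixed true rise of 34.0%, baseline inflation of 5%, 10% or 15% makes the apparent rise 27.6%, 21.8% or 16.5% (for example 1.340/1.10 − 1 = 21.8%). It does not by itself bias a between-arm comparison.

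**Unit of measurement.** These are percentages of steps. Section 10.2.1.3 has the Actigraph software determine bouts of at least moderate activity, and the documents offer no conversion. The shares show scale only and do not predict the loss on the actigraphy measure.

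**The case against.** **No reactivity figure is given, and shrinkage needs Arm 2 to react more than Arm 1.** This stands. The counter is a re-issue, since Arm 2 caregivers wore one at baseline, and reactivity common to both weeks would largely cancel in their own change. A stronger post-week reaction in Arm 2 is plausible, because Arm 1 caregivers have used theirs throughout, but it is an assumption. Scenarios B and C show no loss.

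**Caregiver activity is a minor measure.** This also stands. Section 4.1 makes caregiver data exploratory. Aim 2.5.1 compares caregivers between arms on distress and biological endpoints. Section 13.3 specifies no between-arm test of caregiver actigraphy, so the contrast is implied by the listing in 13.2.4 and not laid down as an analysis.

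**Table 11.1 may describe only continuous wear.** This stands in part. The entry also sits in the baseline column, before anyone is randomised. The diary row carries the same words although all participants record distress there (6.7.2). The table is therefore loose and cannot settle who wears what. If it does govern, Arm 2 caregivers wear no counter and the concern disappears, which is a reason to reconcile the two places.

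**Removing the counter from Arm 2 alone makes the post-week conditions differ by arm.** True, but in Arm 1 the counter is part of the treatment. A control arm without it is the comparison that the kit delay in 6.4.7 implies.

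**Stronger readings that a reader might infer.** One is that the display is known to distort the baseline count and so biases the trial's comparisons. The documents do not show that it does, and a pre-randomisation effect is expected to be balanced. Another is that survivor results are compromised. Survivors in both arms use the same device and walking program, and POMS is not an activity measure.

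**Conclusion.** The point holds as a minor design inconsistency with a possible, unquantified effect on one exploratory measure. Section 6.3.3 gives Arm 2 caregivers a visible step counter in the outcome week, against the intent of 5.2 and 6.4.7 and the apparent sense of Table 11.1.

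On a step scale, the loss of caregiver contrast runs from none to about half (44-54% at the top of the assumed range). The upper end requires four things together: 15% reactivity, reaction in Arm 2 only, an Arm 1 rise of exactly 28-34%, and no anchoring of Arm 1 targets on an inflated baseline. The documents do not support a claim that the contrast will shrink, only that it can. The survivor between-arm comparisons and the primary POMS analysis are not biased.

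**What to change.** 1. Reconcile 6.3.3 with Table 11.1. State that in the post-intervention week Arm 2 caregivers wear the Actigraph only, and correct the table's baseline entry so that it matches what is worn before randomisation.
2. In section 13.3, state that caregiver activity will be compared between arms on post-intervention actigraphy adjusted for baseline, and label it exploratory.

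The cost is a few sentences. There will be no post-week pedometer count for Arm 2 caregivers, and no listed analysis uses one. Their own pre-post change will not be like-for-like, because the counter was worn at baseline but not at the end. That is why the between-arm comparison should rest on adjusted post values.

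Masking the display for everyone in the baseline week is optional. It would restore like-for-like weeks for Arm 2 caregivers, but it is workable only if the devices store counts without the display, which the documents do not show. The baseline count also anchors the walking prescription, so the plan should acknowledge that masking could change that count.

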7. SUBJECT CONSENT AND WITHDRAWAL

- 7.1 Current, state, federal, and institutional regulations concerning informed consent will be followed. Participation in this study is voluntary. Participants are free not to take part or to withdraw at any time, for whatever reason, without risking loss of present or future care they would otherwise expect to receive. In the event that a patient does withdraw from the study, the information they have already provided will be kept in a confidential manner. Participants may discontinue participation in the study at any time if they decide they do not wish to take part any longer. Participants may be withdrawn from the study by research personnel if it is deemed in their best interest to no longer participate.

8. REPORTABLE EVENTS

8.1 *Data and Safety Monitoring*

Clinical Trials Data Safety Monitoring Committee: The Director of the Cancer Center delegates responsibility for continued review and monitoring of all clinical trials conducted by the URCC to the Clinical Trials Data Safety Monitoring Committee. This committee provides oversight of study progress and safety by review of accrual and adverse events at annual meetings. Any adverse event requiring expedited review per protocol will be submitted to the Data Safety Monitoring Committee for determination as to whether further action is required.

The study PI and the study medical monitor determine if the adverse event requires expedited review. Interim meetings are scheduled, as needed, to address specific issues that require immediate attention to assure patient safety.

The Committee:

- a) Reviews assigned clinical trials conducted at the URCC for progress and safety
- b) Reviews all adverse events requiring expedited reporting as defined in the protocol
- c) Reviews reports generated by the URCC data quality control review process
- d) Submits recommendations for corrective actions to the Protocol Review Committee and the PI
- e) In general, outcome data is not made available to individuals outside of the DSMC until accrual has been completed and all participants have completed the intervention. At this time, the DSMC may approve the release of outcome data on a confidential basis to the trial PI for planning the preparation of manuscripts and/or to a small number of other investigators for purposes of planning future trials. Any release of outcome data prior to the DSMC's recommendation for general dissemination of results must be reviewed and approved by the DSMC.

Safety Coordinator: The Medical Director of the Cancer Center Clinical Trials Office appoints the Safety Coordinator. The Safety Coordinator monitors adverse event rates utilizing the URCC Clinical Trials database. If any DSMC assigned study has had two or more of the same SAEs reported in a month or more than six of the same SAEs in six months, the DSMC will review the summary of SAEs, discuss events with the Study Chair, and conduct a more detailed review with the Study Chair. The Data Safety Monitoring Chair will determine if further action is required.

The Safety Coordinator:

- a) Forwards all adverse events requiring expedited reporting to the Data Safety Monitoring Committee Chair who determines if immediate action is required
- b) Maintains a database of all adverse events requiring expedited reporting
- c) Insures all reports are available for all meetings of the Data Safety Monitoring Committee

Protocol date: 7/06/2020

- d) Monitors adverse event rates utilizing the URCC Clinical Trials database.

8.2 *Adverse Reporting Requirements:*

- 8.2.1 Adverse reactions to the EXCAP or EXCAP-PA Exercise Programs will be reported to the University of Rochester Medical Center IRB using the University reporting form and University of Rochester Medical Center adverse event reporting procedures.
- 8.2.2 Serious adverse events, while a participant is on study until 14 days after the date the participant goes off study, will be reported in writing to the IRB as per their requirements.
- 8.2.3 A serious adverse event is defined as any event that is fatal, life-threatening, disabling or incapacitating or results in hospitalization, prolongs a hospital stay or is associated with congenital abnormality, new cancer diagnosis or overdose.
- 8.2.4 This study will make use of the Common Terminology Criteria for Adverse Events (CTCAE), recommended by the National Cancer Institute. These criteria use five grades for adverse events. Grade refers to the severity of the AE. The CTCAE displays Grades 1 through 5 with unique clinical descriptions of severity for each AE based on this general guideline:
- 8.2.4.1 Grade 1: Mild; asymptomatic or mild symptoms; clinical or diagnostic observations only; intervention not indicated.
 - 8.2.4.2 Grade 2: Moderate; minimal, local or noninvasive intervention indicated; limiting age-appropriate instrumental activities of daily living (ADL).
 - 8.2.4.3 Grade 3: Severe or medically significant but not immediately life-threatening; hospitalization or prolongation of hospitalization indicated; disabling; limiting self-care ADL.
 - 8.2.4.4 Grade 4: Life-threatening consequences; urgent intervention indicated.
 - 8.2.4.5 Grade 5: Death related to AE.

